1.1 SUMMARY

Title:	Effect of Structured Progressive Task-Oriented Circuit Class Training With Motor Imagery on Gait in Stroke
Clinical registration no:	NCT03436810
Document Date:	January 18, 2017
Study Description:	Structured Progressive Circuit Class Training (SPCCT) has developed on the basis of task-oriented therapy, provides the enriched benefits on the patients' motivation and motor function. Training with the Motor Imagery (MI) alone can improve gait performance in patients with stroke, but the better effect may observe if combined with the SPCCT. Thus, the aim of this study was to investigate the effect of MI with SPCCT on gait in patients with stroke. The study involved forty patients with stroke from 3 hospitals in Yangon, Myanmar. All participants received the 90 min intervention in a session. The experimental group received MI with SPCCT and control group received HE with SPCCT intervention 3 times a week for 4 weeks. The assessments were taken at the baseline, 2 week and 4 weeks after intervention. The outcomes measures involved spatio-temporal variables, walking endurance, dynamic balance, mobility function and muscle strength.
Objectives:	
General Objective: To investigate the effect of MI with SPCCT on gait performance in patients with stroke
 
Specific Objectives: To investigate the spatio-temporal and functional gait variables in patients with stroke after receiving MI with SPCCT
 
To investigate the spatio-temporal and functional gait variables in patients with stroke after receiving HE with SPCCT
 
To compare the effect of MI with SPCCT and HE with SPCCT on the spatio-temporal and functional gait variables in patients with stroke.

Outcome measures:	Spatio-temporal variables, walking endurance, dynamic balance, mobility function, muscle strength
Study Population:	Forty patients with stroke, age for experimental group was 49.90 ± 11.59 years and control group was 55.55 ± 10.74 years, 15 males and 5 females for experimental group and 11 males and 9 females for control group, Mean height for experimental group was 163.89 ± 6.55 centimeters and control group was 162.03 ± 13.04 centimeters. Mean weight for experimental group was 63.65 ± 6.63 kilograms and control group was 63.35 ± 13.04 kilograms
Description of Sites/Facilities Enrolling Participants:	National Rehabilitation Hospital (NRH), the departments of the Physical Medicine and Rehabilitation in North Okkalapa General Hospital (NOGH) and East Yangon General Hospital (EYGH), Yangon, Myanmar
Description of Study Intervention:	The experimental group received MI with SPCCT and control group received HE with SPCCT intervention 3 times a week for 4 weeks.
Participant Duration:	4 weeks

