1.2 METHODS

Participants

All participants will be diagnosed as a stroke and will be recruited from the departments of the Neuromedical and Physical Medicine and Rehabilitation, Yangon General Hospital (YGH) and the National Rehabilitation Hospital (NRH) in Yangon, Myanmar. Eligible participants will be randomly allocated into either the experimental or control groups. For allocation of the participants, a computer-generated list of random number will be used. In order to maintain recruitment balance between groups throughout the trial, a permuted block randomization process will be used within each strata using block sizes of at least 2 with all blocks divisible by 2. The sequence generation and allocation concealment will be managed by the researcher. To prevent inadequate concealment of allocation sequence, properly randomizing method using sequentially numbered, opaque sealed envelopes (SNOSE) will be used in this study. The allocation envelope will be prepared by using the aluminum foil and carbon paper. The aluminum foil will be used to ensure opaque and the allocation sheet inside cannot read against the light. The carbon paper will be used to prevent violations of allocation concealment. The treatment allocation sheet of standardized-size paper will be fold to fit with envelop. Place 1 sheet of carbon paper on top of the folded allocation sheet with the carbon side facing the paper so that writing on the front of the envelop is transferred to the treatment allocation paper inside. Then place this carbon paper and allocation sheet together inside aluminum foil wrapper. Finally, place complete insert into the envelope properly (290). Group assignment will be communicated directly to the therapist for the implementation on a single participant basis. In this study, the assessments will be done by the researcher. The assessor and the participants will be blinded from the study.

Study Design

The study design will be a randomized double blind balanced parallel-group (1:1).

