Statistical analysis plan

Title: Effect of Structured Progressive Task-Oriented Circuit Class Training With Motor Imagery on Gait in Stroke

Clinical registration no: NCT03436810

Documentt date: January 18, 2017

Statistical analysis plan:

All data will be tested by the SPSS version 18.0 with a significant value of $p < 0.05$ for all comparisons. The demographic data of the participants will be presented with mean, standard deviation, and range for the continuous variables. Frequency and percentage will be presented for the categorical variables.

Normality will be tested by the Kolmogorov Smirnov Goodness of Fit test, for normally distributed variables, a two-way mixed repeated measure ANOVA will be tested to investigate the effect of group and time on the outcome measures. In addition, the interaction effect of the group by time will be detected. For the non-normally distributed variables, the Mann-Whitney U test (between-group) and the Friedman ANOVA test in conjunction with the Wilcoxon Signed-Rank test (within-group) will be used.

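### The motor imagery arm is younger and has more men, apparently by chance, and no planned between-group test adjusts for any baseline covariate

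*Protocol*

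**What the plan says.** Section 1.1 of the protocol (Study Population) gives the ages, "age for experimental group was 49.90 ± 11.59 years and control group was 55.55 ± 10.74 years", and the sexes, "15 males and 5 females for experimental group and 11 males and 9 females for control group". The counts make 20 per arm and 40 in all, which agrees with "The study involved forty patients with stroke from 3 hospitals in Yangon, Myanmar".

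For outcomes judged normal, the SAP states that "a two-way mixed repeated measure ANOVA will be tested to investigate the effect of group and time on the outcome measures", and it adds the group-by-time interaction. For the other outcomes it compares the arms by Mann-Whitney U and looks within arms by Friedman and Wilcoxon tests. Neither branch has a covariate. The baseline measurement enters the ANOVA only as one of the three time points. Age and sex are used for description only: "The demographic data of the participants will be presented with mean, standard deviation, and range for the continuous variables", with counts and percentages for categorical variables.

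The SAP does not say whether the group effect or the interaction decides the result. Nor does it say whether the rank test uses raw follow-up values or changes. Section 1.2 of the protocol says that "a permuted block randomization process will be used within each strata using block sizes of at least 2", but it does not name the strata, and the SAP has no stratum term.

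**The concern.** The outcomes in protocol Section 1.5 are spatio-temporal gait variables, the six-minute walk, the step test, Timed Up and Go and muscle strength by dynamometer. Age and sex plausibly predict all of these. If younger patients and men do better, both gaps push in the same direction, towards MI.

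The planned tests differ in how far they are exposed:

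- **Group main effect, and Mann-Whitney on raw follow-up values.** Both compare levels, so they carry the whole effect of age and sex on level.
- **Group-by-time interaction, or a rank test on changes.** An effect of age or sex that is the same at every visit cancels. What remains is any effect of age or sex on the gain over four weeks.

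Because the SAP leaves open which test decides, a difference in levels could be reported as an effect of MI when part of it reflects who was in each arm.

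**Working it through.** The documents contain no imbalance, power or sample-size calculation, so there is no figure of the plan's own to reproduce. The inputs are the ages and sex counts in protocol Section 1.1, with the ± figures taken as SDs and n = 20 per arm. The 5% level comes from the SAP and is taken as two-sided.

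**1. Age gap.**
- Difference: 55.55 − 49.90 = 5.65 years.
- Pooled SD: √((11.59² + 10.74²)/2) = 11.17.
- Standardised difference: 5.65/11.17 = 0.506.
- t(38) = 0.506/√(2/20) = 1.60, p = 0.12. The 95% interval for the gap is −1.5 to 12.8 years.

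**2. Sex gap.**
- 15/20 − 11/20 = 75% − 55% = 20 points.
- Standardised difference: 0.20/√((0.1875 + 0.2475)/2) = 0.43.
- Fisher p = 0.32; uncorrected chi-square 1.76, p = 0.18.

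**3. Shift in an unadjusted comparison, age alone.** The documents give no correlation between age and any outcome, so r, its size within arms, is assumed.
- Shift in outcome SDs: b = r × 0.506.
- Standard error of the difference: √(2/20) = 0.316 SD.
- Chance of a false result favouring MI, given the gap: 1 − Φ((1.96 − b/0.316)/√(1 − r²)).

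| Assumed r | Shift b (SD) | False result favouring MI, normal approximation | Same, 100,000 simulated t tests |
|---|---|---|---|
| 0.1 | 0.05 | 3.5% | not run |
| 0.2 | 0.10 | 4.7% | 4.6% |
| 0.3 | 0.15 | 6.0% | 5.9% |
| 0.4 | 0.20 | 7.5% | 7.4% |

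The nominal value is 2.5%. For r = 0.2, for example, (1.96 − 0.101/0.316)/√0.96 = 1.67, and the upper tail is 4.7%.

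For comparisons of levels the assumed range is 0.2 to 0.4. For the interaction or a change score the same formula applies, but r is then the correlation of age with change. An assumed 0.1 to 0.3 gives shifts of 0.05 to 0.15 SD.

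**4. Cost in precision of adjusting for age.**
- Share of the age variance explained by arm: 1.60²/(1.60² + 38) = 0.063.
- Variance inflation of the group effect: 1/(1 − 0.063) = 1.067.
- Break-even, where (1 − r²) × 1.067 = 1: r² = 0.063, r ≈ 0.25.
- At r = 0.2 the standard error changes by the factor √(0.96 × 1.067) = 1.01. At r = 0.4 it is √(0.84 × 1.067) = 0.95.
- With sex added, and if age and sex are unrelated in the sample, the inflation is 1/(1 − 0.063 − 1.76/40) ≈ 1.12.

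**The case against.** The case for leaving the plan alone has real force.

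- **Randomisation already protects the test.** Both gaps fit chance at 20 per arm, and the unadjusted comparison keeps its 5% error rate over repeated trials. This stands. A reader might infer that the imbalance shows a failed randomisation or makes the unadjusted analysis invalid, and the documents support neither. The lean is conditional on the imbalance that occurred.
- **The interaction is the natural test of treatment here, and constant effects cancel in it.** This also stands. A reader might carry the 4.6% to 7.4% over to the interaction, but those rates belong to comparisons of levels. Nothing in the documents shows that younger or male patients gain more in four weeks.
- **Choosing age and sex after seeing the gap is post hoc.** This is largely right. Section 1.1 is written in the past tense, which suggests that the data were in hand when it was written. The baseline value of each outcome is a stronger candidate covariate, and it needs no imbalance to justify it.
- **Adjustment may not help precision.** This is right for age when r is below about 0.25, and the assumed ranges lie on both sides of that value.
- **The SAP plans no baseline significance tests.** From "with a significant value of $p < 0.05$ for all comparisons" a reader might infer that the arms would be declared comparable because p is 0.12 and 0.32. The SAP only says that demographic data will be presented, so that criticism is not supported.

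Age or sex may also have been one of the unnamed strata. The documents do not settle this, and the analysis would lack a stratum term either way.

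**Conclusion.** The concern holds as a conditional one. The arms differ by 0.51 SD in age and 20 points in the share of men, and no between-group test in the SAP takes account of either or adjusts for the baseline value as a covariate. If age predicts the level of an outcome at an assumed 0.2 to 0.4, the group main effect or a rank test on raw values leans towards MI by 0.10 to 0.20 SD. The false-positive rate in that direction is then about 4.6% to 7.4% instead of 2.5%. For the interaction the shift is 0.05 to 0.15 SD, and only if age correlates with the gain at an assumed 0.1 to 0.3.

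These figures rest on assumed correlations, on older age meaning worse performance, and on age alone. Sex would add to the lean if men perform better, but the error rates above do not include it. The unadjusted analysis remains valid over repeated trials, so this is an improvement to consider and not a required correction.

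**What to change.** Add to the SAP, for each outcome, a between-group model of the follow-up value (or the change) at each visit, with arm as the factor and the baseline value of that outcome, age (continuous) and sex as covariates. For outcomes judged non-normal, use a rank-based equivalent with the same covariates. Report the adjusted result beside the unadjusted one.

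If outcome data had been seen when this was added, label it a sensitivity analysis and say openly that age and sex were added after the imbalance was known.

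The work is a few sentences and one extra model per outcome, using data the trial already collects. Three covariates reduce the residual degrees of freedom from 38 to 35. The imbalance inflates the variance of the group effect by about 7% for age alone, before any gain from explained variance. Precision therefore improves only if the covariates are sufficiently prognostic (for age, a correlation above about 0.25 in size). The adjusted estimate may also be less favourable to MI.

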1.2 METHODS

Participants

All participants will be diagnosed as a stroke and will be recruited from the departments of the Neuromedical and Physical Medicine and Rehabilitation, Yangon General Hospital (YGH) and the National Rehabilitation Hospital (NRH) in Yangon, Myanmar. Eligible participants will be randomly allocated into either the experimental or control groups. For allocation of the participants, a computer-generated list of random number will be used. In order to maintain recruitment balance between groups throughout the trial, a permuted block randomization process will be used within each strata using block sizes of at least 2 with all blocks divisible by 2. The sequence generation and allocation concealment will be managed by the researcher. To prevent inadequate concealment of allocation sequence, properly randomizing method using sequentially numbered, opaque sealed envelopes (SNOSE) will be used in this study. The allocation envelope will be prepared by using the aluminum foil and carbon paper. The aluminum foil will be used to ensure opaque and the allocation sheet inside cannot read against the light. The carbon paper will be used to prevent violations of allocation concealment. The treatment allocation sheet of standardized-size paper will be fold to fit with envelop. Place 1 sheet of carbon paper on top of the folded allocation sheet with the carbon side facing the paper so that writing on the front of the envelop is transferred to the treatment allocation paper inside. Then place this carbon paper and allocation sheet together inside aluminum foil wrapper. Finally, place complete insert into the envelope properly (290). Group assignment will be communicated directly to the therapist for the implementation on a single participant basis. In this study, the assessments will be done by the researcher. The assessor and the participants will be blinded from the study.

Study Design

The study design will be a randomized double blind balanced parallel-group (1:1).

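### Randomisation is blocked within strata that are never named, and the between-group tests omit them; if the strata are prognostic, those tests are conservative and lose some power.

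*Protocol*

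**What the plan says.** **Design.** Protocol section 1.2 (Participants) plans 1:1 allocation from a computer-generated list and says that "a permuted block randomization process will be used within each strata using block sizes of at least 2 with all blocks divisible by 2". It names neither the factor that defines the strata nor their number, and no other section does.

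**Analysis.** For normally distributed variables the SAP states that "a two-way mixed repeated measure ANOVA will be tested to investigate the effect of group and time on the outcome measures", and adds that "the interaction effect of the group by time will be detected". For other variables it plans Mann-Whitney U between groups, and Friedman with Wilcoxon signed-rank within groups. Testing is "with a significant value of $p < 0.05$ for all comparisons". No stratum or site term appears on either route.

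**Sites.** Section 1.1 (Study Description) says: "The study involved forty patients with stroke from 3 hospitals in Yangon, Myanmar". The site description in the same section names the National Rehabilitation Hospital, North Okkalapa General Hospital and East Yangon General Hospital. Section 1.2 instead recruits from "Yangon General Hospital (YGH) and the National Rehabilitation Hospital (NRH) in Yangon, Myanmar". Only the National Rehabilitation Hospital is on both lists.

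**The concern.** Blocking within strata makes the arms nearly equal inside each stratum, so differences between strata largely drop out of the comparison of arms. A model that does not know about the strata still counts those differences as error. Where they are real, the standard error is larger than the true sampling variation of the group contrast, and the test rejects less often than its nominal level.

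At stake is power in a trial of 40 patients for which the documents give no sample-size calculation. There is also a point of pre-specification: while the factor is unnamed, anyone who later wants to adjust for it must choose it after the fact.

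**Working it through.** The plan states no power, effect size or SD, so there is no figure to reproduce. The check asks how much omitting strata could matter.

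**Inputs from the documents.** Alpha 0.05 (sidedness not stated; two-sided assumed). N = 40, with 20 per arm from the sex counts in section 1.1 (15 + 5 and 11 + 9). Visits at baseline, 2 weeks and 4 weeks (section 1.5).

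**Assumptions.** Three strata of 14, 14 and 12, filled in complete blocks of 2. R² is the share of variance explained by strata. The effect is 0.9 SD for the group main effect and 0.7 SD on each of the two group-by-time contrasts.

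**1. Group main effect, by formula.** R² here refers to the patient's mean over visits. With arms balanced inside strata, the unstratified standard error is too large by a factor 1/√(1 − R²). The true type I error is 2 × [1 − Φ(1.96/√(1 − R²))].
- R² = 0: 5.0%
- R² = 0.1: 1.96/0.949 = 2.066, so 3.9% (standard error 5% too large)
- R² = 0.2: 1.96/0.894 = 2.191, so 2.8% (12% too large)
- R² = 0.3: 1.96/0.837 = 2.343, so 1.9% (20% too large)

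**2. Mixed ANOVA, by simulation.** Type I error in 10,000 trials per row, as without strata / with stratum and stratum by time:

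| R² for level | R² for change over time | Group main effect | Group by time |
|---|---|---|---|
| 0 | 0 | 5.1% / 5.1% | 4.7% / 4.7% |
| 0.1 | 0 | 4.0% / 5.2% | 4.6% / 4.6% |
| 0.2 | 0 | 2.7% / 5.0% | 5.3% / 5.4% |
| 0.3 | 0 | 2.2% / 5.0% | 5.2% / 5.0% |
| 0.2 | 0.1 | 2.9% / 5.1% | 3.3% / 4.7% |
| 0.2 | 0.2 | 3.0% / 5.7% | 2.2% / 4.7% |
| 0.3 | 0.3 | 2.0% / 5.2% | 1.4% / 5.2% |

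The main-effect column agrees with the formula to within simulation error. The group-by-time test uses within-patient error, so differences in level between strata cancel. It becomes conservative only when strata also predict change.

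**3. Power, by simulation.** 5,000 trials per row, without / with strata:

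| R² for level | R² for change | Group main effect | Group by time |
|---|---|---|---|
| 0 | 0 | 78.7% / 78.7% | 80.2% / 79.9% |
| 0.2 | 0 | 81.0% / 87.2% | 78.7% / 78.3% |
| 0.2 | 0.2 | 81.8% / 87.2% | 80.1% / 88.2% |

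A separate simulation of a single change score (40,000 trials per setting, 0.9 SD) gave 80.2% / 83.1%, 81.4% / 87.1% and 82.8% / 91.1% at R² of 0.1, 0.2 and 0.3, and 79.6% / 79.5% at R² = 0.

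**4. Degrees of freedom.** With three strata and three visits, stratum takes 2 between-patient degrees of freedom (error 40 − 2 = 38 becomes 36). Stratum by visit takes 2 × 2 = 4 within-patient degrees of freedom (error 38 × 2 = 76 becomes 72). The R² = 0 row in step 3 shows what this costs when the strata are useless: at most 0.3 percentage points.

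The Mann-Whitney route was not simulated. The same mechanism applies to it, but no size is claimed.

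**The case against.** The strongest reply is that the loss is hypothetical. The documents give no strata and no R², and at R² = 0 nothing is lost. Section 1.2 gives the purpose of blocking as keeping recruitment even between groups, not precision on a prognostic factor. This stands: the size of the loss is conditional throughout. It does not remove the mismatch between a stratified design and an unstratified analysis, and the remedy costs almost nothing if the strata turn out not to matter.

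A second reply is that group by time, the test of differential improvement, is untouched by differences in level. This also stands, and it limits the main-effect figures to the main effect.

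A third is that section 1.2 allows any block size divisible by 2, so incomplete blocks in small strata may leave the arms imperfectly balanced. That is correct. The conservatism figures assume exact balance and would be smaller without it.

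Three stronger readings are tempting, and the documents do not support them:
- A reader might infer that the trial's p-values are too large as a matter of fact. That requires prognostic strata, which cannot be established from the text.
- A reader might infer that every test in the SAP is affected. Friedman and Wilcoxon are within-group tests with no contrast between arms, so this problem does not reach them.
- A reader might infer that hospital is the stratum and that the conflicting site lists therefore bear on precision. Neither document says that hospital is a stratification factor.

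**Conclusion.** The point holds in conditional form. It is certain that the strata are undefined and that the between-group analyses omit them. If the strata explain 10% to 30% of the variance in outcome level, the group main-effect test runs at about 3.9% to 1.9% instead of 5%. At 20% and 0.9 SD it gives up about 6 points of power (81% against 87%). Group by time loses power only if the strata predict change over the 4 weeks: at 20% and 0.7 SD per contrast, about 8 points (80% against 88%). If the strata are not prognostic, the loss is nil.

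These sizes rest on the assumed R², the 14/14/12 split, complete blocks of 2 and the assumed effects; none comes from the documents. The error is in the conservative direction and does not inflate false positives. The conflict between the site lists is a separate documentation defect.

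**What to change.** - **Protocol section 1.2:** name the stratification factor(s) and levels actually used to build the envelope lists. If none were used, say so and remove the reference to strata; the analysis then needs no change on this account.
- **SAP, mixed ANOVA:** add stratum and stratum by visit as fixed terms alongside group, time and group by time. If several factors would create many small strata among 40 patients, enter the factors as main effects (each with its interaction with visit) rather than every combination.
- **SAP, non-normal outcomes:** replace Mann-Whitney U with a van Elteren test stratified by the same factor(s). Name the software if SPSS 18.0 does not provide it. The within-group tests can stay as they are.
- **Separately:** reconcile the recruiting hospitals in section 1.1 with those in section 1.2. If hospital is a stratification factor, the strata cannot be coded until this is done.

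**Cost:** a few sentences of wording and no new data. With three strata and three visits, the model uses 2 between-patient and 4 within-patient degrees of freedom per outcome, a negligible loss of power.
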